Iron deficiency and HMB have been separately associated with decreased quality of life and fatigue in adolescents. HMB in adolescents has been independently associated with fatigue compared to healthy controls [Wang 2013]. Treatment of iron deficiency in non-anemic women has been shown to improve fatigue, especially in women with very low ferritin (<15 ng/mL) [Krayenbuehl 2011]. Iron supplementation has also been shown to increase quality of life and cognitive function [Murray-Kolb 2011]. A large observational study of school children showed a correlation between iron deficiency and

decreased math scores [Halterman 2001]. A randomized trial of oral iron therapy versus placebo in iron deficient adolescent girls demonstrated that those receiving iron supplementation had improved scores on specific cognitive function tests [Bruner 1996].

[figure not shown]
First line therapy for IDA is considered oral iron supplementation [CDC 1998, ACOG 2019]. This recommendation may seem straightforward; however, iron absorption from supplements is generally poor, and significant gastrointestinal side effects can decrease compliance, resulting in worse clinical outcomes [Smith 2014, Tolkien 2015]. Recently, pharmacologic studies have shown promise that alternate day dosing increases the fractional iron absorption per dose. After an individual dose of an iron supplement, an increase in hepcidin (an iron regulatory hormone) is observed and results in decreased subsequent iron absorption for up to 24 hours. Thus recent studies have shown promise that iron absorption is increased when given at 48 hour intervals compared to 24 hour intervals [Stoffel 2017, Stoffel 2019, Moretti 2015]. This data also suggests that less frequent iron supplementation dosing (i.e. with an alternate day regimen) may decrease unwanted side effects while increasing the absorption per dose, resulting in improved treatment compliance. A longer-term, pragmatic trial of iron supplementation comparing daily versus alternate day dosing has not yet been performed.

IB. Objective

- i. *Objective:* To assess the feasibility of performing a randomized trial comparing standard care daily dosing of oral iron to alternate day dosing of oral iron in adolescent girls with iron deficiency anemia (IDA) and heavy menstrual bleeding (HMB).
- ii. *Research Hypotheses:*
 - a. Enrollment will be feasible (>50% of patients who meet eligibility criteria will agree to enroll in the trial).

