 - ii. Gastrointestinal side effects: Participants will be asked a standardized set of questions regarding common side effects of iron therapy (see attachment "GI side effects") [Pereira 2014]
 - iii. Fatigue assessment: NIH PROMIS Pediatric Fatigue – Short Form 10a will be used to assess fatigue at enrollment and each subsequent visit (see attachment "PROMIS Pediatric Fatigue 10a")
 - b. All subjects will complete the following procedures at 4, 12 and 24 weeks:
 - i. Adherence: patients will be asked to bring any remaining pills to the visit and these will be counted as a direct measure of adherence.
 - iv. Concomitant care
 - a. Subjects will be instructed that they should not take a multivitamin containing iron during the study. Otherwise, there will be no limitation on concomitant hormonal therapy, antifibrinolytic therapy, or other treatment of HMB.
 - b. There will be a prohibition of IV iron administration. Any receipt of IV iron prior to 12 week follow up would lead to withdrawal from the study.
 - c. Patients who develop severe anemia requiring pRBC transfusion >7 days after enrollment and prior to 12 week follow up will be removed from the study.
 - d. Other hematologic treatments (i.e. Amicar, Lysteda) will not be directed by or have an effect on the study protocol but will be recorded as part of the study.
 - e. Hormonal therapies (i.e. IV estrogen, combined contraceptive pills, levonorgestrel intrauterine device, etc.) will not be limited but will be recorded as part of the study.

- f. Additional imaging and laboratory studies (pelvic ultrasound, bleeding disorder work up) will not be directed by the study protocol but will be recorded as part of the study.

TIMELINE

Study procedures	Baseline	Week 4 (+/- 3 days)	Week 12 (+/- 1 week)	Week 24 (+/- 1 week)
Screening	X			
Consent/Enrollment	X			
Randomization	X			
Clinical visit	X	X	X	X
*Laboratory studies	X	X	X	X
Medication dispense	X		X	
Adverse effects review		X	X	X
Questionnaires (PBAC, fatigue)	X	X	X	X
Adherence assessment		X	X	X

*Laboratory studies at each visit include: CBC without differential and iron panel

III. Outcomes

IIIA. Primary outcome measures

The primary outcome will be the percentage of eligible patients enrolled.

IIIB. Secondary outcome measures

- i. The following outcomes will be assessed for the pilot study:
 - a. Agreement with randomization (willingness to receive treatment arm assigned)
 - b. Retention (visit follow-up adherence)

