 - c. Adherence (rate of adherence to medication at 12 weeks in both arms based on returned medication volume)
- ii. The following laboratory and clinical data will be collected to inform future clinical trial design (i.e. estimates of variability).
 - a. CBC, iron studies at 4, 12 and 24 week follow up
 - b. Additional laboratory data collected on the patient at enrollment
 - c. PBAC score
 - d. Fatigue score
 - e. Gastrointestinal side effects
 - f. Demographic information at enrollment
 - g. Gynecologic medical and/or surgical treatment
 - h. Hematologic treatment
 - i. Adverse events

IIIC. Sample size

We plan to enroll 40 patients in this feasibility study. This sample size was calculated based on hypothesized feasibility of enrollment and data on patient population of the pediatric gynecology service. On average from July to December 2019, 2-4 patients were admitted to the gynecology inpatient service and 5-10 patients who present to the gynecology outpatient service per month who would meet criteria for enrollment in the study. At minimum, this would mean 84 patients would present over 12 months (7 per month) who would meet eligibility criteria. With an anticipated study

enrollment rate of 50% of eligible patients, it will be reasonable to enroll 40 patients over a 12 month period.

IIIE. Recruitment

- i. The PI will inform all gynecology providers of the study and eligibility criteria prior to study implementation. Two of the PIs are included in a total of ten gynecology providers who practice at the Texas Children's Hospital Main campus (including 4 attendings, 2 nurse practitioners and 4 fellow physicians). Information about the clinical trial will be provided via direct communication by the PI and co-investigators with these practitioners at Texas Children's Hospital.

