- ii. Potential subjects will be identified through review of new patient referrals to Texas Children's Pediatric and Adolescent Gynecology Division, inpatient admissions and/or consultations for HMB. The PI has access to these patient's clinical data as part of routine clinical care and shared patient lists. The outpatient gynecology clinic schedule will be pre-screened daily by the data manager who will notify the PI of potential patients. The PI will assess eligibility and notify the gynecology provider about those subjects who are potentially eligible. The PI or a Co-I will describe the study to eligible patients and their parent/guardian (if less than 18). The voluntary nature of the study will be emphasized.
 - a. If interested in enrollment and meets eligibility criteria, then informed consent will be obtained and the subject enrolled. Patients or parents must provide written, informed consent before any study procedures occur.
 - b. If interested but laboratory evaluation not yet obtained and eligibility unable to be determined at the time of the visit, the PI or a Co-I will obtain a phone number and permission to contact the patient/patient's parent for follow up if eligible. If the patient then meets eligibility criteria and has given permission to be contacted, the data manager will call the patient or her parent to schedule a research only visit within 1 week. At this visit, informed consent will be obtained. Patients or parents must provide written, informed consent before any study procedures occur.
- iii. Screening and enrollment log
 - a. A secure screening and enrollment log will be kept. Each screened patient will be categorized as either: ineligible, eligible but not approached, eligible and enrolled, eligible and declined. If the latter (eligible and declined), the reason for declining will also be obtained and noted in the study log.

IIIF. Allocation

- i. *Sequence generation and concealment:* Participants will be randomly assigned to either the control (daily) or intervention (alternate day) group with a 1:1 allocation per a computer-generated randomization schedule stratified by initial (or post-transfusion if transfusion is given) hemoglobin (less than or equal to 8 g/dL vs greater than 8 g/dL).

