- ii. *Implementation:* The study personnel enrolling the participant will enter the participant's study ID number and enrollment hemoglobin (initial or post-transfusion) into REDCap software programmed for allocation and the software will then assign the subject to an intervention group. The study personnel will then provide information regarding the intervention to the participant, who will not be blinded to the intervention.
- iii. *Blinding:* Due to the nature of the intervention, blinding of participants or staff is not feasible. Every attempt will be made, in the study literature and in training of personnel, to avoid bias of participants related to expected outcomes especially as related to adverse effects. An employee outside the research team will have information regarding the allocated group assignment in a

separate data sheet so the researchers and statistician can analyze data without having access to information regarding the allocation.

IIIG. Data

- i. Collection:* Data on the primary outcome will be collected by study personnel as the number of patients enrolled out of the number of patients approached for enrollment. Secondary outcomes will either be obtained through data entry from the medical record for demographic information, lab results and gynecologic or hematologic treatment received by the patient during the study period. Participants will be assessed for adherence, PBAC score, fatigue score and GI side effects at each subsequent visit.
- ii. Retention:* All reasonable efforts will be made by study investigators and staff to promote participant retention in the study. Data collection will continue on participants who are known to have discontinued the study intervention regardless of reason for discontinuation, which will not be a reason for withdrawal from the study. Participants may withdraw from the study at any time and no additional data collection would be performed on patients who choose to withdraw.

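### Section IIIG.i collects the primary outcome per patient approached, whereas section IIIA defines it as the percentage of eligible patients enrolled

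*Combined protocol and SAP*

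**What the plan says.** Section IIIA defines the outcome: "The primary outcome will be the percentage of eligible patients enrolled". Two other places use the same denominator. The hypothesis in IB.ii.a reads "Enrollment will be feasible (>50% of patients who meet eligibility criteria will agree to enroll in the trial", and the sample-size rationale in IIIC anticipates an "enrollment rate of 50% of eligible patients".

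Section IIIG.i, on data collection, says the primary outcome will be recorded as "the number of patients enrolled out of the number of patients approached for enrollment".

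The recruitment section (IIIE) bears on how far the two groups overlap:

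- IIIE.ii intends eligible patients to be told about the study: "The PI or a Co-I will describe the study to eligible patients and their parent/guardian (if less than 18". Section IVC likewise says that patients meeting the inclusion criteria will be invited.
- IIIE.iii sorts every screened patient into one of four log categories: "ineligible, eligible but not approached, eligible and enrolled, eligible and declined".
- IIIE.ii.b allows contact before eligibility is known: "If interested but laboratory evaluation not yet obtained and eligibility unable to be determined at the time of the visit". Staff then ask for a phone number and permission to call. If the patient proves eligible and has given permission, "the data manager will call the patient or her parent to schedule a research only visit within 1 week".

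Section IIIH says that analyses will be descriptive, with 95% confidence intervals and no formal testing.

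**The concern.** Enrolled over eligible and enrolled over approached are different quantities. The first combines how well the team reaches eligible patients with how often those patients accept. The second leaves out failures of reach.

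The approached group can differ from the eligible group in two ways. It omits eligible patients whom nobody approached, a group the log expressly provides for. It may also include patients contacted before laboratory results who later prove ineligible; the protocol does not say whether such a contact counts as an approach for enrollment. The first difference raises the IIIG.i rate and the second lowers it.

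In a feasibility trial this proportion is the headline result, and IB.ii.a sets more than 50% as the mark of feasible enrollment. If the denominator is still unsettled when the counts are known, the choice between two rates on either side of that mark is open to selective reporting.

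**Working it through.** **Inputs from the protocol.** Eligible patients per month: 2–4 inpatients and 5–10 outpatients (IIIC). Anticipated enrollment rate: 50% of eligible patients (IIIC). Target: 40 (IIIC). Criterion: more than 50% of eligible patients (IB.ii.a).

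**The plan's own figure.** The minimum accrual is (2 + 5) × 12 = 84 eligible patients, and 84 × 0.50 = 42, which supports the target of 40. The sample-size reasoning therefore reproduces on the eligible denominator and does not use the number approached.

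**Relation between the two rates.** Let

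- e = enrolled / eligible (the IIIA rate);
- m = share of eligible patients not approached;
- k = pre-laboratory contacts later found ineligible but counted as approached, per eligible patient.

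Then approached / eligible = 1 − m + k, and the IIIG.i rate = e / (1 − m + k).

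The documents give neither m nor k. Every value below is an assumption.

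**At the anticipated rate, e = 50%:**

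| Assumed share | Missed eligible patients only (k = 0) | Later-ineligible contacts only (m = 0) |
|---|---|---|
| 0% | 0.50/1.00 = 50.0% | 0.50/1.00 = 50.0% |
| 5% | 0.50/0.95 = 52.6% | 0.50/1.05 = 47.6% |
| 10% | 0.50/0.90 = 55.6% | 0.50/1.10 = 45.5% |
| 20% | 0.50/0.80 = 62.5% | 0.50/1.20 = 41.7% |

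The effects cancel when k = m; for example, m = k = 10% gives 0.50/1.00 = 50.0%.

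**In patients.** At 50%, 40 enrolments come from 40/0.50 = 80 eligible patients. If 4 of those 80 (5%) were not approached, the IIIG.i rate would be 40/76 = 52.6%; if 16 (20%) were not, 40/64 = 62.5%.

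**Near the criterion.** A true 48% of eligible patients becomes 0.48/0.95 = 50.5% at m = 5%, k = 0, so a criterion that was missed is reported as met. A true 52% becomes 0.52/1.05 = 49.5% at m = 0, k = 5%, so a criterion that was met is reported as missed.

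**Sampling error, for scale.** The exact 95% interval for 40/80 is 38.6% to 61.4%.

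**The case against.** The strongest reply is that this is a slip of wording in a data-collection paragraph. Section IIIA is the defining section and would govern. IIIE.ii and IVC intend every eligible patient to be approached, so the two denominators may nearly coincide. The log lets the team compute the IIIA rate whatever IIIG.i says, no progression rule depends on the result, and a shift of two or three percentage points is small beside the confidence interval. All of that stands, and it limits the severity. It does not remove the conflict: the log anticipates missed patients, and IIIG.i still gives the analyst a different instruction from IIIA.

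A second reply is that the hypothesis speaks of patients agreeing to enroll, and only patients who are asked can agree, so an acceptance rate may have been meant. That is a plausible intent. However, the sentence still takes patients who meet the eligibility criteria as its denominator, and IIIA does not mention agreement.

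A third reply is that counting pre-laboratory contacts as approached is only one reading. Consent is sought later, at the research-only visit, and the log uses the idea of approach only within the eligible group. This is fair: the downward column of the table depends on that reading, which the protocol neither adopts nor excludes. The upward effect of missed eligible patients does not depend on it.

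**Conclusion.** The concern holds. IIIG.i is out of step with IIIA, IB.ii.a and IIIC, and following it as written would report a different quantity from the declared primary outcome.

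The size cannot be fixed from the documents. With m or k between 0 and 20%, taken one at a time, a true 50% would be reported as anything from 41.7% to 62.5%, and the net direction is uncertain when both operate. Since the anticipated rate is exactly 50% and the criterion is strictly above 50%, a few missed patients can change how the hypothesis is described. What is at stake is the reported primary estimate and that description. The sample size is not affected, and the data are largely recoverable. It should be fixed before the counts are known.

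**What to change.** In IIIG.i, replace the approached denominator with all patients in the screening log determined to be eligible between the start of screening and the close of enrollment. State that this includes those who enrolled, those who declined, those not approached, and those found eligible after a pre-laboratory contact who did not attend the research-only visit.

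Report enrolled over eligible-and-approached as a separately labelled secondary rate. Count the last group as approached, because they had already been asked and had expressed interest. Patients found ineligible then enter neither denominator, which settles the status of pre-laboratory contacts.

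The cost is a change of wording in IIIG.i and one added log label for eligible patients who do not attend the research-only visit, who fit none of the four present categories clearly. Sample size and study procedures are unchanged. The headline rate will be lower than under IIIG.i if missed eligible patients outnumber later-ineligible contacts counted as approached, and higher if the reverse is true. Either way it will be the rate IIIA promises.

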Gastrointestinal (GI) disease, defined as: 
• Serology confirmed celiac disease• Active GI blood loss (gross blood, hemoccult positive stool)	Increased risk of additional causes of anemia
Active malignancy	May cause increased risk of bleeding
Inability to follow-up at TCH	
Receipt of intravenous iron within 30 days prior to enrollment	Expect IDA resolution to occur
Known inability to tolerate oral iron or allergy to oral iron	

IIE. Interventions

- i. Oral iron therapy

- a. At enrollment, patients will be randomized 1:1 between daily versus alternate day dosing of ferrous sulfate 325 mg tablet (65 mg elemental iron). Randomization will occur as described in section III Fi.
 - i. Arm A: ferrous sulfate 65 mg elemental iron once every morning
 - ii. Arm B: ferrous sulfate 65 mg elemental iron once every other morning
 - b. Subjects in both arms will receive an informational handout on how to properly take iron for maximal absorption every 24 or every 48 hours depending on the arm. (Please see attachments "Patient Iron Info Alternate Day" and "Patient Iron Info Daily").
 - c. All subjects will receive a 28 day pill box at enrollment. Subjects in Arm A will receive 100 iron tablets and subjects in Arm B will receive 50 tablets for first 12 weeks of therapy.
 - d. At the end of 12 weeks of oral iron therapy, those subjects with resolution of IDA will be instructed to discontinue iron therapy. Those subjects who have partial or incomplete resolution of IDA will receive next 100 tabs (Arm A) or 50 tabs (Arm B) for continuation of study treatment for an additional 12 weeks.
- ii. Laboratory follow up
 - a. All subjects will have the following labs obtained as part of the study:
 - i. CBC without differential obtained at 4, 12 and 24 weeks (standard of care)
 - ii. Iron panel at 12 and 24 weeks (standard of care)
 - iii. Iron panel at 4 weeks (study purposes, will be obtained with standard of care blood draw and require 0.5-1mL of additional blood drawn)
 - iii. Clinical assessment
 - a. All subjects will complete the following procedures at enrollment, 4, 12 and 24 weeks:
 - i. Menstrual bleeding: Pictorial blood assessment chart (PBAC) will be filled out and score calculated at enrollment and each subsequent visit (see attachment "PBAC") [Sanchez 2012, El-Nashar 2015]

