- iii. Management:* All data will be entered electronically and housed in Texas Children's Hospital REDCap. REDCap is a self-managed, secure, web-based data support system. The data is backed up offsite nightly and hosted in a secure environment maintained by Information Resources. This password protected study database will include a subject's personal identifiers and all Protected Health Information (PHI) such as medical history. All personnel who will be accessing the data will be trained in REDCap and have individual user ID and passwords. Subjects will have a study ID number that will be utilized in lieu of personally identifiable information for all research data provided to statisticians. Documents such as signed informed consent and other paper files will be kept in a locked cabinet that only the PI and her staff have access to in a secure Baylor College of Medicine office building. These files will be maintained in storage for 3 years after completion of the study.

IIIH. Statistical methods

- i.* All planned analyses will be descriptive in nature. Summary statistics such as mean, standard deviation, and 95% confidence intervals will be reported. No formal hypothesis testing will be performed.

IIII. Harms

Significant harms related to the study intervention are not anticipated considering the planned intervention is a commonly prescribed medication that can also be obtained over the counter. The participants may experience discomfort related to common side effects of iron administration including unpleasant taste, nausea, abdominal pain, dark stools, constipation, and/or diarrhea. Participants and their families will be made aware that accidental or intentional iron overdose is a serious potential effect and will be advised to keep iron pills away from small children for the duration of the study. It is possible that subjects randomized to the alternate day intervention may have a slower resolution of iron deficiency anemia. Serious adverse events following initiation of iron supplementation during the study period will be reported to the IRB. Gastrointestinal side effects and adherence will be tracked and will be compared between study groups.

IIIJ. Auditing

After the first subject is enrolled, compliance personnel will audit pharmacy, laboratory and consenting procedures for proper conduct and documentation. Additional audits may occur without warning as warranted by the initial review or spontaneously.

IV. Ethics and dissemination

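### The GI side-effect comparison has no defined summary and no record of when or why iron was stopped, so a per-visit comparison could understate a tolerability difference between arms

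*Combined protocol and SAP*

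**What the plan says.** - **Collection.** Section IIE.iii introduces the clinical assessments with "All subjects will complete the following procedures at enrollment, 4, 12 and 24 weeks". For GI effects it says: "Participants will be asked a standardized set of questions regarding common side effects of iron therapy". The form itself is an attachment. IIIG.i repeats the visit-based schedule: "Participants will be assessed for adherence, PBAC score, fatigue score and GI side effects at each subsequent visit".
- **Participants who stop iron.** IIIG.ii keeps them in follow-up: "Data collection will continue on participants who are known to have discontinued the study intervention regardless of reason for discontinuation". Withdrawal from the study is treated differently: "no additional data collection would be performed on patients who choose to withdraw".
- **Protocol-directed stop.** Under IIE.i.d, after 12 weeks "those subjects with resolution of IDA will be instructed to discontinue iron therapy". These participants still have a week 24 visit.
- **Analysis.** IIII promises the comparison: "Gastrointestinal side effects and adherence will be tracked and will be compared between study groups". IIIH adds only "All planned analyses will be descriptive in nature", with means, standard deviations and 95% confidence intervals and no hypothesis tests.
- **Not stated.** The data list in IIIB.ii has no item for iron stopped, date stopped or reason. The only reason the plan asks for is in IIIE.iii, from eligible patients who decline enrollment. No section says whether the GI summary is per visit or cumulative, or how reports made after stopping are handled.

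**The concern.** The background section argues that GI side effects reduce compliance with oral iron and that alternate-day dosing may ease them. The trial therefore expects symptoms to drive some participants off iron, possibly more of them on daily dosing. A participant who stops at week 6 because of nausea stays in the study, as she should. At week 12 she may report no symptoms and would then count as free of GI effects in her arm. The more often this happens in the less well tolerated arm, the smaller the visible difference becomes.

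Week 24 has a related problem. Participants whose anemia resolved have been off iron since week 12 by protocol, so GI reports at that visit mix people on and off iron. IIII itself allows that resolution may be slower on alternate-day dosing, so the mix may differ by arm.

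At stake are the tolerability estimates that this pilot passes on to the design of a larger trial. The primary outcome, enrollment, is not affected.

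**Working it through.** **Plan figures.** The plan gives no figure for GI effects, so there is none to reproduce. The only plan figure used is the sample size (IIIC): (2 + 5) × 12 = 84 eligible, and 84 × 0.50 = 42, consistent with 40. With 1:1 allocation (IC) that is about 20 per arm.

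**What each planned record can show**

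| Record | Section | Shows when iron was stopped? | Shows why? |
|---|---|---|---|
| GI questions | IIE.iii.a | Not stated | Not stated |
| Pill count | IIE.iii.b, IIIB.i.c | No, only how many tablets were left | No |
| Adverse effects review, adverse events | Timeline, IIIB.ii | Not described | Not described |

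**Model for week 12.** Let e be the share of an arm with GI symptoms on iron, q the share of those who stop because of them, and b the chance that a stopper still reports symptoms at the visit. Assume that symptomatic participants who stay on iron still report. Then

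visit prevalence = e(1 − q) + e·q·b.

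The documents give none of e, q or b. All values below are assumptions.

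| e, A v B | q, A v B | b | Visit prevalence, A v B | Gap (points) |
|---|---|---|---|---|
| 40% v 25% | 0 v 0 | – | 40% v 25% | 15 |
| 40% v 25% | 50% v 20% | 0 | 0.40 × 0.5 = 20% v 0.25 × 0.8 = 20% | 0 |
| 40% v 25% | 40% v 20% | 0 | 0.40 × 0.6 = 24% v 20% | 4 |
| 40% v 25% | 50% v 20% | 0.2 | 20 + 20 × 0.2 = 24% v 20 + 5 × 0.2 = 21% | 3 |
| 40% v 25% | 20% v 20% | 0 | 0.40 × 0.8 = 32% v 20% | 12 |
| 40% v 25% | 50% v 50% | 0 | 20% v 12.5% | 7.5 |
| 60% v 40% | 25% v 10% | 0 | 45% v 36% | 9 (from 20) |
| 60% v 40% | 50% v 10% | 0 | 30% v 36% | −6 (from 20) |
| 60% v 40% | 25% v 25% | 0 | 45% v 30% | 15 (from 20) |

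With equal q and b = 0 the gap shrinks by the factor 1 − q, but the ratio between arms is unchanged. Removing the gap takes clearly unequal stopping.

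**In participants.** At 20 per arm, 40% v 25% is 8 v 5 ever symptomatic. If 4 and 1 of them stop and recover, the visit shows 4 v 4.

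**Precision.** For 40% v 25%, the 95% half-width is 1.96 × √(0.40 × 0.60/20 + 0.25 × 0.75/20) = 1.96 × 0.146 = 0.287, about 29 points.

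**What adherence would show.** Take the same case (20% of Arm A and 5% of Arm B stop) and assume 90% adherence while on iron.
- Stopping at week 6: A = 0.80 × 0.9 + 0.20 × 0.9 × 0.5 = 81%; B = 0.95 × 0.9 + 0.05 × 0.9 × 0.5 = 88%.
- Stopping at week 4: A = 0.72 + 0.20 × 0.9 × 0.33 = 78%; B = 0.855 + 0.05 × 0.9 × 0.33 = 87%.

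A gap of 7 to 9 points would appear, but skipped doses could produce the same one.

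**With stopping for GI symptoms counted as an event.** The cumulative proportion returns to 40% v 25%, provided that stoppers give GI symptoms as the reason.

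**The case against.** The case on the other side has several sound parts.

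- **The recall window is unknown.** If the form asks about the whole period since the last visit, nausea at week 6 is reported at week 12 and most of the week 12 distortion disappears. This stands, and the bias is therefore conditional. It does not help at week 24, where participants with resolved anemia have been off iron for the whole interval. It also does not supply the rate of stopping for GI reasons.
- **Other records exist.** Adherence is compared in the same sentence as GI effects, an adverse effects review is scheduled at weeks 4, 12 and 24, and adverse events are collected. Excess stopping would therefore not go wholly unseen. But the pill count gives no cause and is not linked to the GI result, and the review is not described as recording why iron was stopped.
- **The illustration needs unequal stopping.** This is true, and the documents give no rates to support it.
- **It is a 40-participant descriptive pilot.** Also true: the interval is wider than any shift shown above, which limits the importance of the point.

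A reader might infer that the plan has chosen a biased analysis based on visit prevalence. It has not: it says only that GI effects will be tracked and compared, and the week 4 and week 12 reports needed for a cumulative summary are already collected. Nor is keeping stoppers in follow-up a fault. Symptom burden under the assigned regimen is a legitimate summary and needs those participants.

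**Conclusion.** The point holds as a gap in data capture and in the definition of the GI summary. Nothing listed records when or why iron was stopped, and this cannot be recovered reliably later. Without it, a per-visit GI comparison cannot distinguish an arm that was tolerated from one whose symptomatic participants had stopped.

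The pull toward no difference at week 12 rests on two assumptions: that symptom-driven stopping is greater in the less well tolerated arm, and that the questions cover only recent symptoms. Under the illustrative rates with b = 0, a 15-point gap falls to 0 to 4 points with markedly unequal stopping and to 7.5 to 12 points with equal stopping. The true size is unknown. The week 24 mixture of participants on and off iron depends on neither assumption.

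The documents do not support the stronger conclusion that the less well tolerated arm will look equivalent. That needs assumed, clearly unequal stopping and a reader who ignores the adherence result. This is a minor improvement to a secondary descriptive outcome.

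**What to change.** 1. **Forms, weeks 4 and 12.** Record whether iron was stopped or cut back since the last visit, the date, and the main reason (GI symptoms or other).
2. **IIIH.** Report by arm, with the difference and 95% CI: (a) the proportion who stopped or cut back iron for GI symptoms by week 12; and (b) the proportion with GI symptoms new or worse than at enrollment at week 4 or 12, or who stopped or cut back for GI symptoms.
3. **Supportive summaries.** Keep visit-by-visit prevalence, and show week 24 by whether the participant was still on iron.
4. **Clarify.** State the recall period of the GI questions. Confirm that they are asked at enrollment as IIE.iii.a says, since the adverse effects row of the Timeline starts at week 4 and summary (b) needs the baseline.

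The cost is a few form items at visits already planned, a derived variable for each of (a) and (b), and a few lines in IIIH. No treatment rule changes. The downside is that the reason is self-reported in an open-label trial and may reflect what participants expect of their regimen. Showing (a) separately from (b), with visit prevalence alongside, lets a reader judge how far that matters.
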